9.6 Gender and Ethnicity

Based on previous data from E1996 the anticipated accrual in subgroups defined by gender and race is:

Ethnic Category	Gender		
	Females	Males	Total
Hispanic or Latino	0	2	2
Not Hispanic or Latino	93	157	250
Ethnic Category: Total of all subjects	93	159	252
Racial Category			
American Indian or Alaskan Native	0	2	2
Asian	0	2	2
Black or African American	2	7	9
Native Hawaiian or other Pacific Islander	0	0	0
White	91	148	239
Racial Category: Total of all subjects	93	159	252

The accrual targets in individual cells are not large enough for definitive treatment comparisons to be made within these subgroups. Therefore, overall accrual to the study will not be extended to meet individual subgroup accrual targets.

9.7 Study Monitoring

This study will be monitored by the ECOG-ACRIN Data Monitoring Committee (DMC). The DMC meets twice each year. For each meeting, all monitored studies are reviewed for safety and progress toward completion. When appropriate, the DMC will also review interim analyses of outcome data. Copies of the toxicity reports prepared for the DMC meetings are included in the study reports prepared for the ECOG-ACRIN group meeting (except that for double blind studies, the DMC may review unblinded toxicity data, while only pooled or blinded data will be made public). These group meeting reports are made available to the local investigators, who may provide them to their IRBs. Only the study statistician and the DMC members will have access to interim analyses of outcome data. Prior to completion of this study, any use of outcome data will require approval of the DMC. Any DMC recommendations for changes to this study will be circulated to the local investigators in the form of addenda to this protocol document. A complete copy of the ECOG-ACRIN DMC Policy can be obtained from the ECOG-ACRIN Operations Office - Boston.

10. Pathology Review

NOTE: ECOG-ACRIN requires that all biological samples submitted be entered and tracked via the online ECOG-ACRIN Sample Tracking System (STS). An STS shipping manifest form must be generated and shipped with the sample submissions. See Section [10.5](#).

Rev. 7/11 Pathology materials should be submitted for diagnostic review, classification and correlative studies.

Rev. 7/11
Rev. 4/15

10.1 Pathology Submission

When a patient is registered to receive protocol therapy, the submitting pathologist and clinical research associate should refer to [Appendix](#) (Pathology Submission Guidelines) which provides the following:

10.1.1 Instruction Sheet from ECOG-ACRIN Central Biorepository and Pathology Facility providing details for the Submission of Pathology Materials.

10.1.2 Memorandum to the submitting pathologist from [name]., chair, ECOG-ACRIN Laboratory Science and Pathology Committee, providing details for the Submission of Pathology Materials.

10.1.3 A list of required materials.

10.2 Materials required for this protocol:

Rev. 10/09, 4/15

[Note deleted in Addendum #1]

Rev. 7/11

10.2.1 Sample Tracking System Shipping Manifest Form

Rev. 10/09

In addition to the surgical pathology report, if immunologic studies (ex. flow cytometry) have been performed at the home institution, it is necessary that these be forwarded as well.

Rev. 7/11

10.2.2 Biological Sample Submissions

10.2.2.1 Pathology Review (Mandatory):

Rev. 7/11

Baseline, Weeks 16 and 32, Year 1, and Progression/End of Treatment

Rev. 10/09

- Two (2) stained bone marrow smears to include one (1) Wright-Giemsa (W-G) stain and one (1) Iron Stain

Rev. 10/09

- One (1) H&E stained bone marrow biopsy slide

Rev. 10/09

- One (1) W-G stained peripheral blood smear

Rev. 10/09, 4/15

[Note Deleted in Addendum #1]

NOTE: Submission of pathologic materials for diagnostic review is mandatory in order for the patient to be considered evaluable. Failure to submit pathologic materials may render the case unevaluable.

10.2.2.2 Correlative Studies (Optional Based on Patient Consent)

Paraffin blocks from bone marrow trephine biopsies should be submitted at the following time points:

- Baseline
- Week 16
- Week 32
- Year 1
- Relapse/End of Treatment

NOTE: If blocks cannot be submitted, please submit five (5) unstained bone marrow biopsy level slides. If you have questions, please call [name] at [contact].

Rev. 10/09

Rev. 10/09

Rev. 11/13
Rev. 4/15

10.3 Shipping Procedures

Log the shipment into the ECOG-ACRIN Sample Tracking System (STS) the day of shipment.

Ship using the CBPF's FedEx account using the FedEx on-line ship manager

10.3.1 Submission Schedule

10.3.1.1 The required initial diagnostic materials must be submitted within one month of patient registration. Materials should be submitted within one month of collection for the additional time points.

10.3.1.2 For the blocks for correlative studies, materials should be submitted within one month of collection (Section [10.2.2.2](#)).

Rev. 10/09

Rev. 7/11. 4/15

10.3.2 Shipping Address:

ECOG-ACRIN Central Biorepository and Pathology Facility
MD Anderson Cancer Center
Department of Pathology, Unit 085
Tissue Qualification Laboratory for ECOG-ACRIN, Room G1.3586
[name]
[name]
Toll Free [contact] Local or International Sites)
[contact]
Email: [contact]

Access to the FedEx shipping account for shipments to the ECOG-ACRIN CBPF at MD Anderson Cancer Center can only be obtained by logging onto fedex.com with an account issued by the ECOG-ACRIN CBPF. For security reasons, the account number will no longer be given out in protocols, over the phone, or via email. If your site needs to have an account created, please contact the ECOG-ACRIN CBPF by email at [contact]

An STS shipping manifest form must be generated and shipped with all sample submissions.

10.4 ECOG-ACRIN Central Biorepository and Pathology Facility: Sample Processing and Routing

Rev. 10/09
Rev. 4/15

Pathology review materials for confirmation of diagnosis, pathologic response and at progression will be forwarded to [name]. for review. Materials for the correlative studies will be forwarded to [name] at Moffitt Cancer Center.

10.5 ECOG-ACRIN Sample Tracking System

It is **required** (barring special circumstances) that all biological samples submitted on this trial be entered and tracked using the ECOG-ACRIN Sample Tracking System (STS). All sites, regardless of group affiliation, are required to use the ECOG-ACRIN STS. As of June 2007, the software will allow the use of either 1) an ECOG-ACRIN username or password previously assigned (for those already using STS), or 2) a CTSU username and password.

When you are ready to log the collection and/or shipment of the samples required for this study, please access the Sample Tracking System software by clicking <https://webapps.ecog.org/Tst>.

Rev. 11/13
Rev. 4/15

Important: Please note that the STS software creates pop-up windows, so you will need to enable pop-ups within your web browser while using the software. A user manual and interactive demo are available by clicking this link: <http://www.ecog.org/general/stsinfo.html>. Please take a moment to familiarize yourself with the software prior to using the system.

A shipping manifest form must be generated and shipped with all sample submissions.

Please direct your questions or comments pertaining to the STS to [contact].

10.5.1 Study Specific Notes

Generic Specimen Submission Form (#2981) will be required only if STS is unavailable at time of sample submission. Indicate the appropriate Lab on the submission form:

- ECOG-ACRIN Central Biorepository and Pathology Facility
- ECOG-ACRIN Cytogenetic Laboratory
- [name] Laboratory/H. Lee Moffitt Cancer Center

Rev. 6/11
Rev.4/15

NOTE: When collecting and shipping baseline research specimens (such as bone marrow and peripheral blood), there will be no screening # available. Please note patients must sign consent before the collection of the baseline bone marrow and peripheral blood. Therefore, [name] laboratory [contact]) must be notified of specimen arrival, and then the specimens must be logged into the ECOG-ACRIN STS post-randomization, once the patient has an ECOG-ACRIN sequence number. Please call the receiving laboratories with the ECOG-ACRIN patient sequence number once the patient is randomized.

Retroactively enter all specimen collection and shipping information when STS is available.

10.6 Banking

Residual blocks and/or slides will be retained for banking at the ECOG-ACRIN Central Tissue Repository for possible use in future ECOG-ACRIN approved studies. If future use is denied or withdrawn by the patient, the samples will be removed from consideration for use in any future study.

11. Correlative Studies

Rev. 10/09, 7/11

NOTE: ECOG-ACRIN requires that all biological samples submitted be entered and tracked via the online ECOG-ACRIN Sample Tracking System. An STS shipping manifest form must be generated and shipped with the sample submissions. See Section [10.5](#).

Rev. 6/11
Rev. 4/15
Rev. 7/11

NOTE: Institutions outside of the United States and Canada must confer with the receiving laboratory and the ECOG-ACRIN Operations Office - Boston regarding logistics for submission of fresh samples.

11.1 Cytogenetic Review (Mandatory)

The cytogenetic review will be performed by the ECOG-ACRIN Cytogenetic Laboratory at Mayo Clinic.

Rev. 10/09

NOTE: All study participants/cooperative groups must submit karyotypes to the ECOG-ACRIN Cytogenetic Laboratory as outlined below.

11.1.1 Sample Submission Schedule

Within 30 days of chromosome study for each applicable time point, investigators will send original karyotypes, cytogenetic laboratory report, and completed form #365R to the ECOG-ACRIN Cytogenetic Committee.

Rev. 7/11

Karyotypes must be submitted at:

- Baseline
- Week 16 (after study treatment)
- Week 32
- Year 1
- Relapse/Progression/End of Treatment

Rev. 10/09

Rev. 10/09

NOTE: Karyotypes are required at all time points.

Direct questions to [name] at [contact] or [contact].

11.1.2 Sample Preparation Guidelines

The following materials are to be submitted within one month after each time point:

- Two original karyotypes per clone
- Institution's cytogenetic laboratory report
- The Leukemia Cytogenetics Form (#365R)

11.1.3 Shipping Procedures

Rev. 10/09

Log the shipment into the ECOG-ACRIN STS the day of shipment. If the STS is unavailable, an Generic Specimen Submission Form (#2981) must be submitted with the samples. Once STS is available, retroactively log the shipment into STS, using the actual collection and shipping dates.

The forms and original karyotypes are to be sent to:

[name]

Mayo Clinic Cytogenetics Laboratory
[name]
[name]
[name]
[contact]
[contact]

An STS shipping manifest form must be generated and shipped with all sample submissions.

NOTE: If cytogenetic studies are not successful, submit the laboratory report and #365R form to [name] by mail or fax.

Original karyotypes will be returned upon written request when the review and analysis are complete.

11.2 Additional Laboratory Studies

Biomarker studies described in the Statistical Section that are intended to investigate biological mechanisms of response and resistance to treatment will be performed under the direction of [name] at the Moffitt Cancer Center.

Peripheral blood and bone marrow aspirate samples are requested at the intervals indicated below.

Sample Type	Baseline	Week 16	Week 32	Year 1	Relapse or End of Treatment
Peripheral Blood (Two 10 mL Sodium Heparin tubes)	X	X	X	X	X
Bone Marrow Aspirate (5 mL EDTA tube)	X	X	X	X	X

If you have any questions, please contact [name] or [name] at [contact].

NOTE: If patient has prior documentation of a chromosome 5q deletion, please make note in the comments section of the Sample Tracking System (STS).

11.2.1 Sample Preparation Guidelines

All samples should be clearly labeled with detailed patient information, ECOG-ACRIN Protocol Number, ECOG-ACRIN Patient Sequence Number, Patient Initials, Date, and Type of Sample: Bone Marrow (BM)/Peripheral Blood (PBL).

11.2.1.1 Bone Marrow Aspirate

BM aspirate samples should be collected after coating the syringe with a small amount of preservative-free sodium heparin then transfer it to sterile vacutainer tube(s) containing EDTA preservative (purple tops) for immediate

shipment. The tube must be wrapped in absorbable material and then be placed in an airtight/leakproof container (such as a zip lock bag) and placed in a padded styrofoam container. Express mail envelopes alone are NOT adequate.

11.2.1.2 Plasma

Rev. 10/09

Peripheral blood should be drawn into two (2) standard 10 mL sodium heparin tubes.

11.2.2 Shipping Procedures

Log the shipment into the ECOG-ACRIN STS the day of shipment. If the STS is unavailable, an Generic Specimen Submission Form (#2981) must be submitted with the samples. Once STS is available, retroactively log the shipment into STS, using the actual collection and shipping dates.

Heparinized bone marrow aspirates and plasma should be shipped overnight on cool packs (warm weather months), wrapping the vials to insure that the marrow does not freeze. Specimens must be shipped via next day delivery on the day the specimen is obtained.

Rev. 7/11

DO NOT USE DRY ICE OR WET ICE. During hot summer days, place a cold pack in the container to keep the temperature in the container cool.

Rev. 11/13, 4/15

Ship using the CBPF's FedEx account using the FedEx on-line ship manager.

Access to the FedEx shipping account can only be obtained by logging onto fedex.com with an account issued by the ECOG-ACRIN CBPF. For security reasons, the account number will no longer be given out in protocols, over the phone, or via email. If your site needs to have an account created, please contact the ECOG-ACRIN CBPF by email at [contact]

Call [name] or [name] at [contact] on the day of expected shipment to confirm delivery date.

Shipping Address:

For WEEKDAY Shipping (for ARRIVAL on Monday-Friday):

Rev. 10/09, 4/15

H. Lee Moffitt Cancer Center
[name], [name] Laboratory
[name]
[name]
[name]
[contact]

An STS shipping manifest form must be generated and shipped with all sample submissions.

Rev. 10/09, 4/15

Please only ship on Monday through Thursday. Please do not ship on Fridays or the day before a holiday. Specimens cannot be accepted on the weekends.

11.2.3 Studies to be Performed:

- 11.2.3.1 To evaluate the effect of CD45 isoform profile on lenalidomide enhancement of erythropoietin-induced STAT5 PHN in CD71^{Hi} erythroid precursors and the relation to erythroid response

The goal of the proposed studies is to delineate the value of CD45 isoform profile and the capacity of LEN to augment erythropoietin/STAT5 PHN in CD71^{Hi} erythroid precursors to predict response to study treatment, and to confirm the role of the CD45 PTP as a key negative regulator of the erythropoietin-R signal in non-del5q MDS. We hypothesize that LEN promotes erythropoiesis in non-del5q MDS by relieving CD45 suppression of JAK2/Lyn kinase-mediated STAT5 activation after erythropoietin-R/ligand engagement. Dual features of (a) large CD45 isoform predominance, and (b) enhancement of erythropoietin/STAT5 activation by LEN in CD71^{Hi} erythroid precursors, therefore, may identify non-del5q patients with rhu-erythropoietin resistance and potential responsiveness to LEN treatment. Moreover, these studies will further characterize the impact of CD45 isoform profile on erythropoietin-R signal capacity and erythroid progenitor survival.

To validate this hypothesis, we will assess CD45-RA, -RB and -RO isoform distribution in pretreatment BM erythroid precursors (CD71^{Hi}), and the magnitude of erythropoietin-induced STAT5 PHN in the presence and absence of LEN using a sensitive flow cytometry assay. *Ex vivo* augmentation of STAT5 PHN by LEN in CD71^{Hi} cells (i.e., the *PHN delta*, *PD*) will be quantified by the log₁₀ ratio of p-STAT5 geometric mean fluorescence intensity (MFI) with LEN (LEN)+ erythropoietin versus erythropoietin treatment alone (i.e., LEN+erythropoietin: erythropoietin). CD45 isoform profile in CD71^{Hi} cells will be assessed by the RA:RO and RB:RO isoform geometric MFI ratios. Magnitude of LEN enhancement of erythropoietin/STAT5 PHN (i.e., *PD*) according to CD45 isoform ratio and the linkage between isoform ratio and LEN associated reduction in erythroid apoptotic fraction will be evaluated as a continuum to determine the *PD* and isoform ratio associated with a threshold necessary for clinical response and augmentation of erythroid survival. Moreover, the capacity for LEN augmentation of STAT5 activation will be confirmed *in vivo* by comparing STAT5 PHN intensity in erythroid precursors by immunohisto-chemistry in fixed BM biopsy sections from pre-treatment and week16, post-treatment BM specimens. Because our investigations indicate that the erythropoietic effects of LEN in non-del5q MDS are erythropoietin-dependent, clinical resistance to

LEN monotherapy (Arm A) may arise from endogenous erythropoietin under-production despite evidence for *ex vivo* erythropoietin/STAT5 activation. PB plasma erythropoietin concentration will be assessed prior to treatment and at week 16 of LEN monotherapy by enzyme-linked immunosorbant assay (ELISA) and the findings correlated with treatment response and results of *ex vivo* p-STAT5 *PD* in the pre-treatment BM specimen. The proposed studies will be the first to characterize the erythropoietin-R signal axis in MDS, its regulation by a key PTP, and the application of a pharmacodynamic model to identify patients responsive to a targeted therapeutic in a large, uniformly treated MDS population. Moreover, primary and secondary treatment failure specimens provide a valuable resource to explore mechanism(s) of treatment resistance and the relationship to erythropoietin-R signal suppression.

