9.5 Statistical Analysis for Correlative Studies

We expect that at least 60-70% of samples collected for correlative studies will be adequate for analysis. The statistical plan for the first and the third aim is based on the assumption of 132 patients (62% samples of 212 patients randomized before May 19, 2010 and after September 24) are available for analysis of correlative studies. The statistical plan for the second aim is based on the assumption of 16 del5q31.1 patients (62% samples of 26 del5q31.1 patients enrolled to the study) are available for analysis of correlative studies.

- 9.5.1 Evaluate the effect of CD45 isoform profile on lenalidomide enhancement of erythropoietin-induced STAT5 phosphorylation in CD71^{Hi} erythroid precursors and the relationship to erythroid response.

The association between the CD45 isoform profile and ex vivo augmentation of STAT5 phosphorylation by lenalidomide will be assessed by simple regressions. The phosphorylation delta (PD) as quantified by the log₁₀ ratio of p-STAT5 geometric mean fluorescence intensity (MFI) with lenalidomide (LEN)+ erythropoietin versus erythropoietin treatment alone (i.e., LEN+erythropoietin:EPO) will be regressed on RA:RO, RB:RO ratios separately. With 132 non-del5q31.1 patients, there is 83% and 94% power to test this association at a two-sided significance level of 0.05, if the true but unknown correlation between PD and RA:RO (or RB:RO) ratio is 0.25 and 0.3 respectively. The relationship between the CD45 isoform profile and MER response status will be assessed by treatment arm. RA:RO and RB:RO ratios will be compared between MER responders and non-responders within each treatment arm using the Wilcoxon rank sum test. The same assessment will be performed on the relation between PD and MER response status, and on the relation between apoptosis reduction and MER response status.

Prior studies show that response rate to erythropoietin varies for patients with different serum erythropoietin levels. To investigate if the addition of DA benefits the group of patients with sub-optimal erythropoietin production at baseline, MER response rates will be compared between treatment arms in the subset of patients with low serum erythropoietin levels at baseline (defined as <500 mU/ml) using Fisher's exact test. Furthermore, to investigate if primary resistance to lenalidomide monotherapy is due to low endogenous erythropoietin production, the change in serum erythropoietin levels at 16 weeks

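### Section 11.2.3.1 seeks a two-feature predictor of response and a threshold, but Section 9.5.1 relates MER to one marker at a time and plans no threshold analysis

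*Combined protocol and SAP*

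**What the plan says.** Section 11.2.3.1 gives the purpose of the CD45/STAT5 work as establishing the value of two measurements "to predict response to study treatment". Its hypothesis pairs them: "Dual features of (a) large CD45 isoform predominance, and (b) enhancement of erythropoietin/STAT5 activation by LEN" in CD71-high erythroid precursors may pick out non-del5q patients who resist erythropoietin and could respond to lenalidomide. The laboratory work is then described as validating that hypothesis. The markers are to be examined on a continuous scale to find the PD and "isoform ratio associated with a threshold necessary for clinical response and augmentation of erythroid survival". The section closes by describing the work as the "application of a pharmacodynamic model to identify patients responsive to a targeted therapeutic".

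Section 9.5.1 provides these analyses for the aim:

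- **Marker with marker.** PD "will be regressed on RA:RO, RB:RO ratios separately". MER is not in these regressions.
- **Marker with response.** "RA:RO and RB:RO ratios will be compared between MER responders and non-responders within each treatment arm using the Wilcoxon rank sum test". Then: "The same assessment will be performed on the relation between PD and MER response status", and likewise for apoptosis reduction.
- **Other.** Serum erythropoietin comparisons, and regressions linking ex vivo PD to in vivo activation.

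The planned sample is "132 patients (62% samples of 212 patients randomized before May 19, 2010 and after September 24"), about 66 per arm. The power statements for this aim concern correlations between markers. Multiplicity control in Section 9.5 is written only for the chromosome 5q and related lesion analyses.

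**The concern.** The laboratory section asks whether two features, taken together, identify responders, and at what values. The statistical section asks whether each marker, taken alone, differs between responders and non-responders. A set of one-marker tests cannot show whether PD adds anything once the isoform ratio is known, or the reverse. It cannot separate either feature mattering from both mattering together, and it produces no cut-off.

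Two things are at stake. First, the aim's own question stays unanswered even if every planned test is carried out. Second, the promised threshold has no method behind it. A cut-off picked after looking at response, and then described by its performance in the same patients, tends to look far better than it is. It could be carried into later work as a patient-selection rule.

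**Working it through.** **1. The plan's own power figures.** For a correlation tested two-sided at 0.05, power = Φ(atanh(r)·√(n−3) − 1.96).

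| n | r | Calculation | Power | Stated |
|---|---|---|---|---|
| 132 | 0.25 | 0.2554 × √129 − 1.96 = 0.94 | 82.7% | 83% |
| 132 | 0.30 | 0.3095 × √129 − 1.96 = 1.56 | 94.0% | 94% |
| 66 | 0.35 | 0.3654 × √63 − 1.96 = 0.94 | 82.7% | 84% |
| 66 | 0.40 | 0.4236 × √63 − 1.96 = 1.40 | 92.0% | 93% |

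A noncentral-t calculation gives 83.8%, 94.8%, 84.8% and 93.7%. The stated figures are right, but they are power to detect that two markers correlate. None is power for MER.

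**2. Numbers available for response.** 0.62 × 212 = 131.4, taken as 132, or 66 per arm. At the design rates in Section 9.2 (30% and 50%) that is about 20 responders in Arm A and 33 in Arm B, 53 in all.

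**3. What an uncorrected threshold would look like.** *Assumption:* the plan gives no procedure, so this takes one that silence permits. One cut is searched over the inner 80% of a marker that has no relation to response. At each cut k, z = (p_high − p_low)/√[p(1−p)(1/k + 1/(n−k))]. The data set counts as significant if the largest |z| exceeds 1.96. The Youden index is sensitivity + specificity − 1, with true value 0. Results from 20,000 simulated data sets per row:

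| n | Responders | Nominally significant | Mean apparent Youden |
|---|---|---|---|
| 66 | 20 | 40% | 0.22 |
| 66 | 33 | 44% | 0.20 |
| 132 | 53 | 42% | 0.15 |

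Independent repeats stayed within 40-45%. If both cuts of a two-marker rule are searched on a decile grid (marker correlation 0.25), the false-positive rate is 51% with 20 responders of 66 and 57% with 33 of 66.

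**4. Does a joint test gain power?** *Assumptions:* n = 66, normal markers with correlation 0.25. Under the first two forms MER is 60% when both markers exceed the true cut and 25% otherwise. Under the additive form each marker contributes about 0.5 log-odds per SD. The joint test is Fisher's exact test on a both-above-median indicator.

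| True form | One Wilcoxon test | At least one of two (unadjusted) | Both-above-median indicator |
|---|---|---|---|
| Both above the median | 33% | 50% | 60% |
| Both above the 35th percentile | 40% | 59% | 43% |
| Additive | 59% | 79% | 48% |

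Repeat runs moved most entries by about 3 points. The additive single-marker figure ranged from 53% to 59%. The indicator wins only when its cut coincides with the true one. Under the additive form it is worse than a single-marker test.

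**5. What a model could deliver.** Fitted within one arm of 66, with odds ratios of 1.5 to 2.0 per SD for each marker and for their product, the 2-df joint test of both markers has 53-89% power. The test of the product term has 26-49%. A pooled model with an arm term has 53 expected responders for three coefficients (arm, isoform ratio, PD), 53/3 ≈ 18 each.

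**The case against.** The strongest defence is that objective 2.2.8.2 asks only for the effect of the CD45 profile on STAT5 phosphorylation and its relationship to erythroid response. Section 9.5.1 analyses both parts. The pairing of features and the threshold appear only in the laboratory narrative, and there in tentative wording. This is a consent-based mechanistic aim, and the MER comparison, sample size and interim rules do not depend on it. All of that is correct and limits the weight of the point. It does not remove the mismatch, because the same narrative says it will validate the hypothesis and determine a threshold.

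Three stronger readings are tempting, and the documents do not support them:

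- *The plan claims that response occurs only when both features are present.* It says the features may identify certain patients. The wording also allows an additive reading, or one feature marking erythropoietin resistance and the other lenalidomide responsiveness.
- *The plan commits to an uncorrected cut-point search on the same patients.* It does not. It speaks of examining the markers on a continuum and gives no procedure. What can be said is that no method, and no separate or resampled validation data, are described.
- *Single-marker tests will usually miss a joint effect.* Step 4 shows that this depends on the assumed form. Power figures at n = 132 would not help either, since every planned marker-response test is within arm.

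**Conclusion.** The concern holds as a mismatch between two sections. Section 11.2.3.1 sets a two-feature question and promises a threshold. Section 9.5.1 never assesses the two features together against MER and plans no threshold analysis or validation. That follows from the text and needs no simulation.

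The 40-45% false-positive rate and the apparent Youden index of 0.15-0.22 show the risk if a cut-off is chosen and judged on the same patients without correction. They rest on that assumption and on a search over the inner 80% of the marker. The power comparison supports modelling the markers together on their continuous scale. It does not support making a median-split indicator or a product term the main test. The aim is secondary and correlative, and the primary analysis is unaffected. The change is still worth making because the aim cannot otherwise answer its own question.

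**What to change.** Add two items to Section 9.5.1.

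1. **Joint model.** Fit a logistic regression of MER on isoform ratio and PD together, both continuous, with a term for arm. Fit it once for RA:RO and once for RB:RO, matching the existing regressions. Report the 2-df joint test of the two markers and each marker's contribution given the other. Keep the product term, or a both-features indicator fixed without looking at response, as a supportive analysis only.
2. **Threshold rule.** Label any PD or isoform-ratio threshold exploratory. Report it with bootstrap optimism-corrected sensitivity and specificity and a bootstrap interval for the cut-off, with the selection step repeated in each resample. Give no p-value at the selected cut.

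Section 11.2.3.1 should then refer to these analyses. The cost is a few lines of text and slightly more programming, with no new samples. The corrected accuracy figures will look less favourable than uncorrected ones.
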